Days from randomization	≤30	—	15	29	43	57	71	85	99	113	N/A	* = visit may be conducted remotely or on site, per preference of the study site or participant. See Section 4.1 for details about remote visits.
Visit interval tolerance (days)	—	—	±3	±3	±3	±3	±3	±3	±3	±3	N/A	±3
Eczema Area and Severity Index (EASI)	X	X		X				X		X	X	
Body Surface Area (BSA)	X	X		X				X		X	X	
Laboratory Tests and Sample Collections												
Hematology	X			X			X		X	X		
Clinical Chemistry	X			X			X		X	X		
Urinalysis	X			X			X		X	X		
Serum pregnancy	X											Only for women of childbearing potential (Section 8.2.3.1 and Appendix 10.4).
Urine pregnancy (local)		X		X		X		X	X			Only for women of childbearing potential (Section 8.2.3.1 and Appendix 10.4).
HIV screening tests	X											
Hepatitis C Virus (HCV) screening tests	X											HCV RNA will be measured to confirm positive hepatitis C virus antibody

Notes:												

 Visit 1 procedures may be conducted over more than 1 day as long as all activities are completed within the allowable visit tolerance. For early terminations (ETs) that occur before the last visit in treatment period, see the activities listed for ET in this table. Visit 801 is only for study participants who are terminating early or not rolling into the long-term extension study (DRM06-AD07/J2T-DM-KGAA). 												
Visit number	1	2	3*	4	5*	6*	7*	8	9*	10	ET	V801*
Weeks from randomization	Screening (-4)	Baseline /Day 1	2	4	6	8	10	12	14	16	ET	Safety follow-up Week 26 (or approximately 12 weeks after last study drug injection)
Days from randomization	≤30	—	15	29	43	57	71	85	99	113	N/A	* = visit may be conducted remotely or on site, per preference of the study site or participant.
Visit interval tolerance (days)		—	±3	±3	±3	±3	±3	±3	±3	±3	N/A	See Section 4.1 for details about remote visits.
												(Section 8.2.6).
Hepatitis B Virus (HBV) screening tests	X											Includes testing for HBsAg, anti-HBc, and anti-HBs.
HBV DNA	X							X				Only for participants who are anti-HBc reactive and anti-HBs nonreactive at screening (Section 8.2.5).
Total IgG	X											
Total IgA	X											
Anti-tetanus toxoid IgG antibody		X					X		X			At Week 12, collect this sample before the vaccine administration.
Meningococcal Group C serum bactericidal antibodies (human complement serum bactericidal assay)		X					X		X			At Week 12, collect this sample before the vaccine administration.

Notes:												

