6.1. Study Interventions Administered

6.1.1. Study Drugs

This study involves administration of lebrikizumab and placebo, as shown:

Study Drug Name	Lebrikizumab	Placebo ^b
Dosage Formulation	250 mg (2 mL) ^a	To match lebrikizumab
Dosage Levels and Frequency	Baseline and Week 2: 500 mg loading dose Weeks 4-14: 250 mg Q2W	To match lebrikizumab
Routes of Administration	subcutaneous injection	subcutaneous injection

Abbreviation: baseline = randomization (Visit 2); Q2W = once every 2 weeks.

^a All study drug (lebrikizumab and placebo) will be supplied as a sterile prefilled syringe with needle safety device (PFS-NSD). Each prefilled syringe is intended for a single 2 mL dose (250 mg) administered subcutaneously.

^b Placebo solution is identical in appearance and content to the active solution except for lebrikizumab.

For drug administration information, see Sections 6.1.3 and 6.1.4.

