
then participants stay in the study to:
 
 • complete all the remaining study visits and assessments through Week 16 
AND
 
 • roll into the long-term extension study, if entry criteria are met 
OR
 
 • undergo the safety follow-up visit (V801). 	
then participants will not stay in the study and
 
 • undergo an ET visit 
AND
 
 • the safety follow-up visit (V801).

If the study drug is permanently discontinued before Week 12 and participants are continuing in the study, these study participants will not receive the vaccines at Week 12.

See the SoA for assessments to be performed at the time of the ET visit and safety follow-up. In addition to the SoA, safety follow-up is outlined in Section 8.2 (“Safety Assessments”) and Section 8.3 (“Adverse Events and Serious Adverse Events”) of the protocol.

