9.3. Populations for Analyses

The following participant populations are defined:

Population	Description
Intent-to-Treat (ITT)	All participants assigned to study drug, regardless of whether they take any doses of study drug, or if they took the correct study drug. Participants will be analyzed according to the treatment group to which they were randomly assigned.
Per Protocol (PP)	All participants in the safety population who complete the Week 16 (Visit 10) evaluation without any significant protocol violations.
Safety	All participants randomly assigned to study drug and who take at least 1 dose of study drug. Participants will be analyzed according to the study drug they actually received.
Pharmacokinetic Analysis	All randomized participants who received at least 1 full dose of

	study drug and at least 1 postbaseline evaluable PK sample.
Immunogenicity Analysis	A participant is evaluable for treatment-emergent ADA if there is at least 1 non-missing test result for ADA for both the baseline and the postbaseline visits.

Abbreviations: ADA = anti-drug antibody; PK = pharmacokinetic.

The PP population will include participants in the safety population without significant protocol deviations (i.e., any participant or investigator activity that could have possibly interfered with the therapeutic administration of the study drug or the precise evaluation of the study drug efficacy). Significant protocol deviations include the following:

- Used prohibited treatment that required permanent discontinuation of the study drug (see Section 7.1.2)
- Missed either one or both Week 12 or Week 16 study visits (Visits 8 and 10)
- Have not been compliant with the dosing regimen (i.e., participants must receive 80% of the expected injections of study drug and both of the vaccines during participation in the study)
- Exceeded the out-of-the-visit window at the Week 16 visit (Visit 10) by more than ± 7 days

Additional significant protocol deviations may be specified in the Statistical Analysis Plan (SAP) prior to unblinding.

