HIPAA	Health Insurance Portability and Accountability Act
HIV	human immunodeficiency virus
hSBA	human complement serum bactericidal assay
hulgG4	humanized monoclonal immunoglobulin G4 antibody
IB	Investigator's Brochure
ICF	informed consent form
ICH	International Council for Harmonisation
IEC	Independent Ethics Committee
IFN-γ	interferon gamma
IgA	immunoglobulin A
IGA	Investigator Global Assessment
IgE	immunoglobulin E
IgG	immunoglobulin G
IL	interleukin
Informed consent	A process by which a participant voluntarily confirms his or her willingness to participate in a particular study, after having been informed of all aspects of the study that are relevant to the participant's decision to participate. Informed consent is documented by means of a written, signed and dated informed consent form.
INR	international normalized ratio
investigational product	A pharmaceutical form of an active ingredient or placebo being tested or used as a reference in a clinical trial, including products already on the market when used or assembled (formulated or packaged) in a way different from the authorized form, or marketed products used for an unauthorized indication, or marketed products used to gain further information about the authorized form.
IRB	Institutional Review Boards
ITT	intention to treat: The principle that asserts that the effect of a treatment policy can be best assessed by evaluating on the basis of the intention to treat a participant (that is, the planned treatment regimen) rather than the actual treatment given. It has the consequence that participant allocated to a treatment group should be followed up, assessed, and analyzed as members of that group irrespective of their compliance to the planned course of treatment.
IUD	intrauterine device

Term	Definition
IUS	intrauterine hormone-releasing system
IWRS	interactive web-response system
LLOQ	lower limit of quantitation
LOR	loricrin
LTBI	latent tuberculosis infection
MCMC	Markov Chain Monte Carlo
MCV	Meningococcal (Groups A, C, Y, and W-135) Oligosaccharide Diphtheria CRM197 Conjugate Vaccine (GlaxoSmithKline)
MRCP	magnetic resonance cholangiopancreatography
non-WOCBP	women of nonchildbearing potential
NRS	Numeric Rating Scale
Participant	Equivalent to CDISC term “subject”: an individual who participates in a clinical trial, either as recipient of an investigational medicinal product or as a control
PFS-NSD	prefilled syringe with needle safety device
PK	pharmacokinetics

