6.10.1. Primary Outcome and Methodology

The primary analysis of the study is to confirm that lebrikizumab 250 mg Q2W is the same as placebo when evaluating the booster response to the Tdap vaccine and the response to positive antibody response to MCV (Group C serum bactericidal antibodies) (proportion of participants) at Week 16 in the PPS population.

The primary estimand addresses the treatment response as directed. A 90% CI for the difference of proportion between treatment groups will be constructed using the stratified Newcombe approach (Yan and Su 2010; Kim and Won 2013) for each of the coprimary endpoints separately. Missing values will not be imputed. Descriptive statistics of antitetanus toxoid IgG antibody concentration (including the number of participants, mean, standard deviation, median, minimum, maximum, geometric mean, and coefficient of variation) and Meningococcal Group C serum rSBA titers (including the number and percentage of participants in each titer level) at Week 0, Week 12, and Week 16 will also be provided.

Primary outcomes booster response to the Tdap vaccine and the response to positive antibody response to MCV (Group C serum bactericidal antibodies), and the analysis are described in [Table KGAK.6.6](#).

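### A participant who is vaccinated at Week 12 and then permanently stops study drug for a non-rescue reason leaves before the Week 16 titers, so both co-primary outcomes are lost

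*Protocol*

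**What the plan says.** The table at the end of Protocol Section 7.1.2 separates two groups after permanent discontinuation of study drug. Those who stopped because of systemic rescue remain to "complete all the remaining study visits and assessments through Week 16". For everyone else, "then participants will not stay in the study"; they have an ET visit and then V801, with content set by the SoA.

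The SoA gives each vaccine serology three marks: baseline, Week 12 and Week 16. The comment on the second is "At Week 12, collect this sample before the vaccine administration". SAP Section 6.10.1 agrees, because titer summaries "at Week 0, Week 12, and Week 16 will also be provided" and no other time point is named.

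Both co-primary endpoints need the value 4 weeks after vaccination (Protocol Section 3). Missing values are not imputed (Protocol 9.4.2; SAP 6.10.1). The per-protocol exclusions in Protocol 9.3 include "Missed either one or both Week 12 or Week 16 study visits (Visits 8 and 10"), and the supplementary mITT analysis in SAP Table KGAK.6.7 is as observed.

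**The concern.** The retention rule works against the primary analysis. It keeps systemic-rescue participants to Week 16, although the per-protocol definition excludes them. It sends out participants who were on drug when immunized, have had both vaccines and have met the dosing rule. It also separates people with the same exposure: Section 7.1.1 envisages that a participant whose drug is temporarily withheld can continue visits through Week 16, whereas one whose stop is labelled permanent leaves, even if each misses only the Week 14 injection.

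The missing value follows a post-randomization event. The listed reasons for stopping include low white cell or lymphocyte counts, serious or opportunistic infection and drug-related hypersensitivity. These could plausibly be related to antibody response and could differ between lebrikizumab and placebo. The mITT analysis cannot serve as a check on the per-protocol result for this selection, because the same people lack titers in both.

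**Working it through.** **1. The plan's own precision.** Inputs from Protocol 9.2: 109 per arm, 83% (tetanus) and 90% (MCV) in both arms, two-sided 90% Wald interval. Half-width = 1.645 × √(2p(1−p)/109).
- Tetanus: 1.645 × √(2 × 0.83 × 0.17/109) = 0.0837, stated as 0.08.
- MCV: 1.645 × √(2 × 0.90 × 0.10/109) = 0.0668, stated as 0.07.

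Both reproduce. The planned loss is 240 − 218 = 22, or 9.2%.

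**2. Injections by Week 12.** Protocol 6.1.1: "Baseline and Week 2: 500 mg loading dose Weeks 4-14: 250 mg Q2W", and "Each prefilled syringe is intended for a single 2 mL dose (250 mg) administered subcutaneously". A 500 mg dose is therefore two injections.
- Planned: 2 + 2 + 6 (Weeks 4, 6, 8, 10, 12, 14) = 10.
- Through Week 12: 2 + 2 + 5 = 9, so 9/10 = 90%, above the 80% in Protocol 9.3. (Protocol 9.4.1.4 uses 100% as its compliance definition and should be reconciled, but the per-protocol rule is the 80% one.)

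After the Week 14 injection no drug remains to be stopped, so the rule has effect only between the Week 12 and Week 14 doses.

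**3. Titers at ET.** The SoA columns are displaced in the available text, so this is a reading of the spacing of marks. Hematology, PK and EASI each have a further mark directly after Week 16. The two serology rows do not, and SAP 6.10.1 names only Weeks 0, 12 and 16.

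**4. Effect on precision.** The documents give no rate of stopping in this window. Assume 1%, 2%, 3% or 5% of 240, which is 2.4, 4.8, 7.2 or 12 people split evenly between arms.

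| Assumed rate | Tetanus, kept in addition to 109 per arm | Tetanus, lost beyond the planned 22 | MCV, kept | MCV, lost |
|---|---|---|---|---|
| 1% | 0.0832 | 0.0842 | 0.0665 | 0.0672 |
| 2% | 0.0828 | 0.0846 | 0.0661 | 0.0676 |
| 3% | 0.0823 | 0.0851 | 0.0658 | 0.0680 |
| 5% | 0.0815 | 0.0861 | 0.0651 | 0.0688 |

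The largest change is 0.0861 − 0.0837 = 0.0024.

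**5. Effect of selective loss.** Suppose m people are lost from one arm, in addition to 109 observed.
- If all m were non-responders, the rate with them included is 109p/(109 + m). For m = 2, 4, 6 the shift is −1.5, −2.9, −4.3 points (tetanus) and −1.6, −3.2, −4.7 points (MCV).
- If all m were responders, the rate is (109p + m)/(109 + m). At m = 6 the shift is +0.9 points (tetanus) and +0.5 points (MCV).

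**6. Width of best-case and worst-case bounds.** With m lost per arm and equal observed rates, the extremes of the difference are ±m/(109 + m): 2/111 = 1.8, 4/113 = 3.5 and 6/115 = 5.2 points.

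**The case against.** The strongest reply is that the primary analysis is meant to be restricted. SAP 6.2.1 declares a principal stratum estimand with intercurrent events captured through the population definition. A reader might infer that the analysis hides its conditioning, but the documents state it. SAP 6.6 also lists every randomized participant who stopped study treatment, with reason and timing. This stands. The remaining gap is that no planned output links those stops to vaccination and missing titers or bounds their effect.

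Other stronger readings are tempting and not supported:
- *The rule contradicts the protocol's ITT definition.* The words that participants "participant allocated to a treatment group should be followed up, assessed, and analyzed as members of that group irrespective of their compliance" come from the abbreviations list and describe a general principle. The operative ITT population in Protocol 9.3 says who is counted and in which arm; it promises no follow-up.
- *Only the missed Visit 10 keeps these people out of the per-protocol set.* Among the listed criteria that is so, but the list is open. Protocol 9.3 and SAP Table KGAK.6.1 allow further deviations, and stopping drug during the response period could be one.
- *Every non-rescue stop is affected.* Protocol 7.2 and 7.2.1 allow approved exceptions, and vaccine-related hypersensitivity does not stop study drug.
- *An ET visit inside the Week 16 window draws no titer.* This is not established. Nothing prevents such attendance being run as Visit 10, and Protocol 4.1 pairs Visit 10 with ET, though only for visit type.
- *Many are affected, mostly because of adverse events.* Neither has a source. Protocol 7.1.2 calls permanent discontinuation rare, and 7.2 expects discontinuation to be uncommon. If the 22 planned losses were spread evenly over 16 weeks (an assumption), two weeks would hold 22 × 2/16 = 2.75 from all causes, including consent withdrawals that no rule recovers. The 5% scenario, 12 people, would be 12/22 = 55% of the planned loss and is unlikely.

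**Conclusion.** The concern holds as a cheap improvement. The retention rule is poorly aligned with the co-primary outcomes, because it can remove a vaccinated participant with 90% of the injections before the only post-vaccination draw, and no planned analysis recovers the value. The affected window is about two weeks and the number is unknown, probably a few. Precision is not the issue. If losses concentrated in one arm and were all non-responders, two to four of them would move that arm's rate by about 1.5 to 3 points against a half-width of roughly 7 to 8. That is worth reporting but would not by itself dominate the result, and the study is descriptive with no hypothesis test (Protocol 9.1).

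This rests on reading the SoA as having no ET titer, on full dosing through Week 12, and on assumed stopping rates. A reader might infer that an amendment could still repair this trial. It cannot: SAP 6.16 shows that the Week 16 lock has occurred and that MCV retesting uses specimens already collected.

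**What to change.** **For the protocol, or a later study using this template:**
- In Section 7.1.2, ask participants who received the Week 12 vaccines and later stop study drug to attend Visit 10 for the two vaccine serologies before safety follow-up. Exempt those who have withdrawn consent or are subject to mandatory study withdrawal, for example for pregnancy or unblinding.
- Align Section 7.2, which at present ends study participation together with study intervention.
- State in the SoA that an ET visit inside the Week 16 window draws both titers. An earlier ET draw would not supply the 4-week value; attendance at Week 16 is what matters.
- Leave the drug-stopping criteria unchanged.
- Use the resulting titers at least in the as-observed mITT analysis, and say whether these participants count in the per-protocol set.

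**For this trial:** report, by arm and reason, the vaccinated participants without a Week 16 titer, and give best-case and worst-case bounds on each co-primary difference.

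**Cost:** a short amendment where one is still possible, one extra attended visit for a few participants who have stopped drug (the visit and draw already exist), and a small amount of extra analysis.

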7.2. Participant Discontinuation/Withdrawal from the Study

A participant may withdraw from the study:

- at any time at his/her own request
- at the request of his/her designee (for example, legal guardian)
- at the discretion of the investigator for safety, behavioral, compliance, or administrative reasons
- if the participant becomes pregnant during the study (see Section 8.3.5 and Appendix 10.4, Section 10.4.3)
- if enrollment in any other clinical study involving an investigational product or enrollment in any other type of medical research judged not to be scientifically or medically compatible with this study
- if the participant, for any reason, requires treatment with another therapeutic agent that has been demonstrated to be effective for treatment of the study indication, discontinuation from the study occurs prior to introduction of the new agent

The participant must be discontinued from the study:

- if an investigator, site personnel performing assessments, or participant is unblinded

NOTE: In cases where there are ethical reasons to have the participant remain in the study, the investigator must obtain specific approval from the sponsor-designated medical monitor for the participant to continue in the study.

Discontinuation is expected to be uncommon.

At the time of discontinuing from the study, if possible, an ET visit should be conducted, as shown in the SoA. See SoA for data to be collected at the time of study discontinuation and follow-up and for any further evaluations that need to be completed. The participant will be permanently discontinued both from the study intervention and from the study at that time.

If the participant withdraws consent for disclosure of future information, the sponsor may retain and continue to use any data collected before such a withdrawal of consent. If a participant withdraws from the study, he/she may request destruction of any samples taken and not tested, and the investigator must document this in the site study records.

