6.5.3. Rescue Treatment for Atopic Dermatitis

During this study, add-on rescue therapies may be needed if the participant experiences clinical worsening of symptoms that are intolerable.

Participants will be eligible to receive rescue treatment with any locally approved AD treatments at the discretion of the investigator. Investigators are encouraged to provide rescue therapy in a staged fashion, using a greater intensity of treatment compared to that which the participant was using, for example:

- high-potency TCS, or
- treating with:
 - oral corticosteroids
 - systemic nonsteroid immunosuppressants, or
 - phototherapy.

Refer to Section 7.1.2 for discontinuation criteria associated with systemic rescue treatment.

Participants using topical or systemic rescue medication who complete the study through Week 16 will be eligible to continue to a separate long-term extension study after the Week 16 visit has been completed.

All rescue treatment usage must be captured in the eCRF.

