7.1.2. Criteria for Permanent Discontinuation of Study Drug

In rare instances, it may be necessary for a participant to permanently discontinue (definitively discontinue) study drug.

Possible reasons for permanent discontinuation of study intervention

Possible reasons that may lead to permanent discontinuation of the study drug include, but are not limited to, the following:

Investigator decision

- The investigator decides that the participant should be discontinued from study drug. Some examples may include:
 - Inter-current illness that would, in the judgment of the investigator, affect assessments of clinical status to a significant degree
 - Treatment-related AEs that are clinically significant, deemed persistent, in the judgment of the investigator
 - Unacceptable toxicity

Systemic hypersensitivity reaction

- If the investigator, after consultation with the sponsor-designated medical monitor, determines that a systemic hypersensitivity reaction has occurred related to study drug administration, the participant should be permanently discontinued from the study drug.
- If a participant experiences a hypersensitivity event determined by the investigator to relate to the vaccine products, the participant will not be permanently discontinued from the study drug.

Required reasons for permanent discontinuation of study intervention

Permanent discontinuation of study drug should occur in the following instances:

Use of systemic rescue treatment

- If a participant receives rescue treatment with a systemic corticosteroid, immunosuppressant, or phototherapy, the participant must permanently discontinue study drug.
- Participants who receive rescue treatment with topical steroids may continue treatment with study drug.

NOTE: Participants who discontinue study drug due to rescue medication use should continue to attend all study visits through Week 16 and be assessed for safety and efficacy according to the SoA (as shown in the table at the end of this subsection).

Hepatic event or liver test abnormality

- Participants who are discontinued from the study drug due to a hepatic event or liver test abnormality should have additional hepatic safety data collected via eCRF. Discontinuation of the study drug for abnormal liver tests **should be** considered by the investigator when a participant meets one of the following conditions after consultation with the sponsor-designated medical monitor (see Section 8.2.7):
 - ALT or AST ≥ 8 times ULN

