6.4.1. Markov Chain Monte Carlo Multiple Imputation

The method of handling missing efficacy data as mentioned in [Table KGAK.6.4](#) will be as follows for both binary and continuous endpoints.

For participants who receive rescue medication (high-potency topical corticosteroids [TCS] or systemic AD treatment, defined in [Appendix 2](#)) or discontinue from the study treatment due to lack of efficacy, values should be set to the participant's baseline value subsequent to this time through Week 16. The Markov chain Monte Carlo multiple imputation (MCMC-MI) will be used to handle the remaining missing data. Imputation will be conducted within each treatment group independently so the pattern of missing observations in 1 treatment group cannot influence

missing value imputation in another. The SAS PROC MI with the MCMC option will be used to conduct the MCMC-MI. The imputation model will include the relevant baseline and postbaseline.

For each imputation process, 25 datasets with imputations will be calculated. The initial seed values are given in [Table KGAK.6.5](#). Each complete data set will be analyzed with the specified analysis. The results from these analyses will be combined into a single inference using SAS PROC MIANALYZE.

For binary responses related to the Eczema Area and Severity Index (EASI) and IGA, the binary response variables will be calculated based on the multiply imputed datasets that have been created. Because the MCMC algorithm is based on the multivariate normal model, imputed values for IGA will not generally be one of the discrete values used in IGA scoring (0, 1, 2, 3, or 4). Therefore, to derive the binary IGA response variable, standard rounding rules will be applied to the imputed values. For example, if a participant has an IGA score imputed as 1.4 (and assuming a baseline IGA score of 3), the imputed value would be rounded down to 1, and the minimum change from baseline of 2 would have been met. This participant would be considered a responder.

For derivation of a $\geq 75\%$ reduction from baseline in EASI score (EASI 75) and $\geq 90\%$ reduction from baseline in EASI score (EASI 90) response, no rounding will be performed. The imputed Week 16 EASI value will be compared directly to the observed baseline EASI value to determine whether a reduction of at least 75% or 90% was achieved.

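### Protocol 7.2 has a participant who needs another AD treatment leave the study, while 6.5.3 and 7.1.2 keep rescued participants in it to Week 16; the MCMC-MI results and the per-protocol set can depend on which text a site followed

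*Protocol*

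**What the plan says.** Protocol 7.2 lists circumstances in which a participant leaves the study. One is needing, for whatever reason, another treatment shown to work in AD; in that case "discontinuation from the study occurs prior to introduction of the new agent". The bullet makes no exception for rescue and does not refer to 6.5.3 or 7.1.2. The list opens with "A participant may withdraw from the study", and a separate list of mandatory exits contains only unblinding. The section adds that a participant who leaves stops both study intervention and study.

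Protocol 6.5.3 says "Participants will be eligible to receive rescue treatment with any locally approved AD treatments at the discretion of the investigator". It also says "Participants using topical or systemic rescue medication who complete the study through Week 16 will be eligible to continue" into the extension study. Under Protocol 7.1.2, systemic rescue ends study drug, but "Participants who discontinue study drug due to rescue medication use should continue to attend all study visits through Week 16"; the table closing that section has them "complete all the remaining study visits and assessments through Week 16". For topical rescue, "Participants who receive rescue treatment with topical steroids may continue treatment with study drug".

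In SAP 6.4.1, values after rescue (high-potency topical corticosteroid or systemic AD therapy, Appendix 2), or after stopping treatment for lack of efficacy, are set to baseline. Multiple imputation by MCMC "will be used to handle the remaining missing data". SAP 6.2.2 and Table KGAK.6.3 place every other discontinuation reason under a hypothetical strategy: set to missing, then imputed as if treatment had continued. Protocol 9.4.3.1 has the same structure, with systemic rescue only.

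**The concern.** One event, AD that needs another treatment, has two written dispositions. If the participant stays, the event is rescue and the composite strategy applies. If the participant leaves, there is an early termination visit and the safety follow-up visit (V801), and the analysis depends on the recorded reason for stopping. Neither 7.1.2 nor 7.2 names lack of efficacy among its reasons, and nothing says how an exit made in order to start another AD therapy should be coded.

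Two things are at stake. First, Table KGAK.6.7 makes MCMC-MI the secondary (main) analysis for IGA 0/1, EASI-75, EASI-90 and the Pruritus NRS endpoints. Under that method the same treatment failure could be a non-responder on one route and a partial responder on the other. Second, membership of the per-protocol set (PPS), used for the co-primary vaccine endpoints, can depend on the route for users of topical rescue.

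**Working it through.** **1. The event traced through each analysis rule.**

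| SAP method | Rescued, stays (7.1.2) | Leaves (7.2), coded lack of efficacy | Leaves (7.2), other code |
|---|---|---|---|
| MCMC-MI (6.4.1, Table KGAK.6.3) | baseline value | baseline value | missing, then imputed |
| NRI (6.4.4) | non-responder | non-responder | non-responder |
| MMRM (6.4.2) | later values missing | later values missing | later values missing |
| LOCF (6.4.3) | later values missing, then carried forward | same | same |

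Only one cell differs: MCMC-MI with a code other than lack of efficacy.

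**2. Size of that difference.** A participant set to baseline cannot be a responder. Let a share x of an arm fall in the differing cell, with mean imputed response probability r. The arm's response rate rises by x × r. The documents give neither quantity, so both are assumptions.

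| x | r = 0.1 | r = 0.3 | r = 0.5 |
|---|---|---|---|
| 2% | 0.2 points | 0.6 points | 1.0 points |
| 5% | 0.5 points | 1.5 points | 2.5 points |
| 10% | 1.0 points | 3.0 points | 5.0 points |

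With 240 / 2 = 120 randomized per arm, 2% to 10% is 2.4 to 12 participants. The modified ITT set is smaller by the two excluded sites, whose numbers are not given. The treatment difference moves by x × r on lebrikizumab minus x × r on placebo, so equal values in both arms cancel.

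**3. PPS membership.** Table KGAK.6.1 excludes users of systemic rescue, and anyone who missed the Week 12 or Week 16 visit.

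- Systemic rescue, stays: excluded as a prohibited-treatment deviation.
- Systemic therapy needed, leaves before Week 16: excluded for the missed visit.
- High-potency topical rescue, stays on study drug: can remain in the PPS.
- The same participant, leaves under 7.2 before Week 16: excluded for the missed visit.

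Only the topical group changes status.

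**4. Effect on co-primary precision.** The plan's own figure first. The half-width of the Wald 90% interval with 109 per arm is 1.645 × sqrt(2p(1 − p)/109).

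- Tetanus, p = 0.83: 0.0837, stated as 0.08.
- MCV, p = 0.90: 0.0668, stated as 0.07.

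Both reproduce. If 2% to 10% of the 109 were lost by the topical route (assumption), n per arm falls to 106.8 to 98.1. The half-widths become 0.0845 to 0.0882 for tetanus and 0.0675 to 0.0705 for MCV. For scale, the planned loss from randomized to per-protocol is 22/240 = 9.2%.

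**The case against.** The best reply is that the conflict is softer than the 7.2 bullet suggests. Its list is permissive, the mandatory list is separate, and 7.1.2 addresses rescue by name in both a note and a table. The natural reading is that the specific rule governs, and nothing in the documents shows a site doing otherwise. This has weight but does not settle the matter. The bullet's own wording is directive. Pregnancy stands in the same permissive list, yet Protocol 8.2.3.1 and 10.4.3 make that exit compulsory, so a site cannot take the lead-in to mean that every item is optional.

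A reader might infer that the two routes always give different imputations. They do not: three of the four methods agree, and MCMC-MI agrees too when the code is lack of efficacy.

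A reader might also infer that a participant who leaves has no rescue on record. The Schedule of Activities collects concomitant therapy at early termination and again at V801. What stays open is whether therapy recorded then triggers the rescue rule, because SAP 6.1.2 ends the treatment period at the early termination visit.

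Nor do the documents support a claim that the problem falls mainly on placebo, or that it favours lebrikizumab. If it did fall mainly on placebo, placebo response would rise and the apparent benefit would shrink.

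Finally, little rests on it: Protocol 9.1 calls the study descriptive, Protocol 7.2 expects discontinuation to be uncommon, the co-primary endpoints are not imputed, and NRI or MMRM supplements most of the MCMC-MI endpoints. That limits the importance but leaves the inconsistency in place. Lost Week 16 skin scores matter little, since the SAP replaces post-rescue values or sets them to missing on either route. The loss bears more on safety follow-up and on as-observed vaccine data for exits after Week 12.

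**Conclusion.** The inconsistency is real: the 7.2 bullet and the rescue provisions of 6.5.3 and 7.1.2 give different dispositions for the same event, and no text says which prevails. The analytic consequence is conditional. It reaches the MCMC-MI results only through exits coded to something other than lack of efficacy, where it shifts an arm's response rate by 0.2 to 5.0 percentage points for affected shares of 2% to 10% and imputed response of 0.1 to 0.5. It reaches the co-primary analysis only through topical rescue users dropping from the PPS. Under the assumed losses the effect on precision is small, at most 0.0045 on the tetanus half-width (0.0882 − 0.0837). All these shares are assumptions; the true number of such exits is not in the documents and may be very small. The point is worth correcting because the correction is cheap and removes a dependence on site interpretation.

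**What to change.** **Protocol.** 7.2 must be reconciled with 6.5.3 and 7.1.2 so that one rule governs whether a rescued participant stays to Week 16. Which rule is a clinical matter on which this review takes no position. The Week 16 lock was set for when the last participant had completed Week 16 or early termination, so new wording can no longer change conduct in the treatment period. The clinical study report should state how such cases were handled.

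**SAP 6.2.2 and 6.4.1.** Add one rule: any exit from study or treatment made in order to start another AD therapy that meets the Appendix 2 rescue definition is assigned to the composite category (set to baseline), whatever reason is coded. Report the number of these exits by arm.

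**Status.** SAP Version 3 was approved after the Week 16 database lock, at which an unblinded analysis was performed. The rule should be labelled as added after unblinding, or run as a sensitivity analysis beside the existing MCMC-MI result.

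**Cost.** A protocol clarification, one SAP sentence, a review of the discontinuation and concomitant-therapy records, and one count by arm. No new data collection is needed.
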